14.8.2. Laboratory Parameters

Incidence of abnormalities for clinical laboratory assessments (chemistry and hematology) will be summarized by visit. Laboratory analytes and their changes from baseline will be summarized by visit.

14.8.3. Physical Examinations and Vital Signs

Adverse physical examination changes will be reported as AEs and analyzed as such. Vital signs and their changes from baseline will be summarized by visit.

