2.6. Rationale for the Overall Design

This is a Phase 2/3 open-label, multicenter study to assess the safety and efficacy of ORGN001 in neonates, infants, and children with MoCD Type A.

A placebo-controlled study is not feasible or ethical due to the severity of the untreated disease and reports of improved outcomes in MoCD Type A neonates treated with rcPMP; also, the lack of available treatment precludes inclusion of an active control arm. ORGN001 safety will be reviewed continuously, on an individual patient basis, as well as at a group level. An SRC,

[REDACTED]
[REDACTED] will review all available safety, efficacy and PK data on a periodic basis.

In neonate patients with signs and symptoms consistent with MoCD Type A, treatment should be initiated as soon as feasible, in an effort to prevent the irreversible neurologic damage that is expected to occur. Less frequently, older infants and children may present with neurologic

symptoms related to MoCD such as seizures, movement disorder, and developmental delay/disability that appears to have a less rapidly evolving course.

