3.2. Endpoints

Primary Efficacy Endpoint:

- Overall survival (OS)

Secondary Efficacy Endpoints:

- Changes in growth parameters (height, weight, body mass index (BMI), head circumference) through Month 12
- Feeding pattern assessments through Month 12
- Gross Motor Function Classification System Expanded and Revised (GMFCS-E&R) results through Month 12
- Assessments of the Bayley Scales of Infant Development – Third Edition (Bayley-III) Cognitive and Motor Scales as measured through Month 12

- For children aged 3 and above, for whom the Bayley-III is no longer appropriate, the Wechsler Preschool and Primary Scale of Intelligence – Fourth Edition (WPPSI-IV) will be administered.
- For patients with severe developmental delay, the WPPSI may not be an appropriate assessment, and therefore, the Bayley-III may be administered instead.
- Functional ability and activities of daily living, measured by the Pediatric Evaluation of Disability Inventory (PEDI) through Month 12
- Gross Motor Function Measure (GMFM)-88 results through Month 12

[REDACTED]

[REDACTED]

[REDACTED]

Safety Endpoints:

- The type, frequency, severity, timing, and relationship to study drug of any AEs, serious AEs (SAEs), and changes in vital signs, electrocardiograms, and safety laboratory tests

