4.3. Study Assessments

No study procedures may be performed prior to obtaining informed consent. Screening/Baseline and Day 1 assessments may all occur on the same day.

For neonates born prior to 37 weeks of gestation, the Month 12 assessments will be performed at the target time point, adjusted for prematurity by scheduling the visit date plus the addition of the difference between gestational age and full-term gestation of 40 weeks.

Results of all study assessments will be recorded in the appropriate case report form (CRF). Analyses of study assessments are described in [Section 14](#).

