7.2. Patient Inclusion Criteria

Patients must meet all of the inclusion criteria to be considered eligible for enrollment in this study.

- Male or female neonatal patients (1 to 28 days of age [inclusive] at the time of ORGN001 administration, with day 1 of age corresponding to the day of birth), or infant (29 days to < 2 years of age) or child (2 to 5 years of age [inclusive]) with MoCD Type A, previously untreated with ORGN001 or treated with ORGN001 through the EAP
- In neonates, diagnosis of MoCD Type A, based on:
 - Prenatal genetic diagnosis, or
 - Onset of clinical and/or laboratory signs and symptoms consistent with MoCD Type A (eg, seizures, exaggerated startle response, high-pitched cry, axial hypotonia, limb hypertonia, feeding difficulties, elevated urinary sulfite and/or SSC, elevated xanthine in urine or blood, or low or absent uric acid in the urine or blood) within the first 28 days after birth
- In infants or children, diagnosis of MoCD Type A, based on:

- Confirmed genetic diagnosis (genetic confirmation of the diagnosis of MoCD Type A may be obtained after initiation of ORGN001 therapy in certain cases), biochemical profile, and clinical presentation consistent with MoCD Type A
- Parent or legal guardian must have signed the ICF prior to any study procedures being performed

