14. STATISTICAL METHODS AND PLANNED ANALYSES

Assessments will be binned into analysis visits in such a way that the assessment closest to the target study day among all assessments observed within a window around the target day will be designated for analyses over time. The visit windows will span from above the midpoint of the target day and prior visit target day up to and including the midpoint between the target day and next visit target day.

All data collected during the study will be presented in data listings, tables, and figures as described below. Continuous variables will be summarized using mean, SD, median, minimum, and maximum. Categorical variables will be summarized using percentages and frequency distributions. Confidence intervals will be provided for all means and percentages to aid in interpretation.

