14.8. Safety Analyses

Safety analyses will be performed on the Safety Set, which includes all patients who receive at least 1 dose of ORGN001.

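### By-visit mean changes in vital signs and laboratory values pool entry ages from day 1 to 5 years with no stated age reference, so they can reflect maturation and age mix

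*Combined protocol and SAP*

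**What the plan says.** Section 3.2 names "changes in vital signs, electrocardiograms, and safety laboratory tests" within the safety endpoint. The group analysis of two of these is one sentence each. For vital signs (14.8.3): "Vital signs and their changes from baseline will be summarized by visit". For laboratory values (14.8.2): "Laboratory analytes and their changes from baseline will be summarized by visit", beside a by-visit incidence of chemistry and hematology abnormalities.

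The population is a single set (14.8): "Safety analyses will be performed on the Safety Set, which includes all patients who receive at least 1 dose of ORGN001". Section 14 lists mean, SD, median, minimum and maximum for continuous variables and adds: "Confidence intervals will be provided for all means and percentages to aid in interpretation".

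Neonates enter from day 1 of age, and sections 4.1 and 7.2 admit infants from 29 days and children up to 5 years. Patients already treated with ORGN001 under expanded access may enrol. Section 4.1 schedules a 12-month period and then Months 13 to 36. On a control arm, section 2.6 says: "A placebo-controlled study is not feasible or ethical due to the severity of the untreated disease".

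**The concern.** Subtracting baseline removes differences in level between patients. It does not remove the change that a growing child would show anyway, and that change depends on the age at which follow-up starts. Over 12 or 36 months, a patient first dosed as a newborn and one first dosed at 5 years pass through different stretches of development, yet both enter the same visit mean.

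Two things follow for the later visits. The mean change can differ from zero with no drug effect. It can also differ from one visit to the next because the proportion of neonatal entrants has changed, with no change in any patient's course. A confidence interval supplied as an aid to interpretation invites the reader to take a shift away from zero as a finding about ORGN001. At stake is the readability of the stated group summary for two components of the safety endpoint.

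**Working it through.** The plan gives no figure on this point, so there is nothing to reproduce. The check sets the texts side by side and then uses simple mixture arithmetic.

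**1. Ages in one visit row.** Age at a visit is entry age plus time on study. Taking 5 years as the upper entry age, Month 12 covers ages from about 1 year (day 1 + 12 months) to 6 years (5 + 1). Month 36 covers about 3 years to 8 years (5 + 3).

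**2. Does the plan itself expect maturation?** Yes, for the kidney. The population PK model in section 2.5 carries a term for maturing renal function in neonates, and section 4.1 ties neonatal dosing to gestational age, citing renal clearance. Creatinine and blood urea nitrogen are safety analytes (4.3.8, 13.3). Their mean change by visit therefore includes a process that the plan models elsewhere.

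**3. Where does the plan allow for age?**
- Growth: converted to age-adjusted z-scores and percentiles (14.7.3).
- Efficacy: analysed in neonate and pediatric sets as well as the Full Analysis Set (14.7).
- Preterm neonates: "the Month 12 assessments will be performed at the target time point, adjusted for prematurity" (4.3). For gestational age below 37 weeks, the shift to 40 weeks is more than 40 − 37 = 3 weeks.
- Vital-sign and laboratory tables: none stated. Natural history data are placed under efficacy (14.7.1), and no readable text brings them into these tables.

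**4. Effect of age mix.** Let p be the share of neonatal entrants at a visit, and N and O the mean changes in neonatal and older entrants. Then

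pooled mean change = p·N + (1 − p)·O,

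and a move of dp in the share shifts it by dp·(N − O). A 10-point move shifts it by 10% of N − O. With assumed counts, one neonate leaving an even mix of 6 takes p from 3/6 = 0.500 to 2/5 = 0.400 (10.0 points). In an even mix of 20, p goes from 10/20 = 0.500 to 9/19 = 0.474 (2.6 points). Section 14.1 sets no minimum sample size, so small visit counts are possible.

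**5. Illustration with zero drug effect.** All inputs here are assumed; none is in the documents. Work in units of the within-group SD of change, so that

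pooled SD = √(1 + p(1 − p)(N − O)²).

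Take N = 2, O = 0, p = 0.5:
- Mean = 0.5 × 2 = 1.0. SD = √(1 + 0.25 × 4) = 1.41.
- n = 12: 95% CI 0.10 to 1.90.
- n = 8: 95% CI −0.18 to 2.18.

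Over N = 1 to 3, O = 0 to 0.3 and p = 0.25 to 0.75, the pooled mean runs from 0.25 × 1 = 0.25 to 0.75 × 3 + 0.25 × 0.3 = 2.33 SD. This shows the mechanism. It does not estimate the size in this trial.

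**The case against.** **Weight.** No test, stopping rule or success criterion uses these means, and the layout of descriptive safety tables in a small single-arm study is partly a matter of taste. This stands and sets the level of the point.

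**Inference from silence.** That the tables are raw and pooled is read from the absence of any split or standard. Sections 14.8.2 and 14.8.3 show no redaction, but parts of 4.3.6 and 13.2 do, and naming one Safety Set does not bar age displays within it. This stands as a caution. Still, the efficacy sections name age subsets and age scores, and the safety sections name neither.

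**Existing safeguards.** Individual data are listed (14), investigators judge the significance of abnormal laboratory results (13.3), significant test findings are recorded as adverse events (13.5.1), and the Data Monitoring Committee sees all safety data (6.2). Medians and ranges accompany the means, and demographics are summarised for the Safety Set (14.4). These protect patients, but they do not make a pooled mean change easier to attribute.

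**Stronger readings that the documents do not support.**
- A reader might infer that a safety signal will be created or hidden. The intervals in the illustration exclude zero at n = 12 and include it at n = 8, on assumed inputs; nothing in the documents settles which would occur.
- A reader might use the ratio of age at visit to age at entry as a measure of bias. It measures no vital-sign or laboratory effect and grows without limit as entry age nears zero: at Month 12, (28 + 365)/28 = 14.0 but (1 + 365)/1 = 366.
- A reader might infer that laboratory abnormalities will be judged against the wrong limits. Section 14.8.2 does not name the limits, which is missing detail and not evidence of wrong ones.

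**Conclusion.** The point holds as a limit on interpretation. Following the plan as written gives mean changes, with intervals, that can reflect maturation and age mix as well as any effect of ORGN001. The direction and size for any analyte or vital sign cannot be derived from the documents, and no mmHg or laboratory figure should be attached to it.

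It rests on two assumptions: that the tables are produced as the readable text describes, and that patients of clearly different entry ages are enrolled. If nearly all entrants were neonates, the mix problem would shrink but maturation would remain.

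It is not an error in a figure. The primary analysis of overall survival and the patient-level safety review are unaffected. It is a cheap improvement.

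**What to change.** Keep the pooled tables and add the following to the statistical methods.

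1. **By-visit tables by age group** (neonate, infant, child) at first ORGN001 dose, for vital signs and laboratory values. Identify patients pretreated under expanded access separately and state their baseline. The only readable definition of baseline (14.7, under efficacy) is the last assessment before ORGN001 treatment, which for these patients may precede study entry. Note under the tables that the split reduces mixing but does not remove maturation within a group, since infants span 29 days to under 2 years.
2. **Age-referenced heart rate and blood pressure**, where norms exist: z-scores, percentiles, or counts outside the age-specific range. Compute them at actual age at the reading, corrected for prematurity, because visits are assigned by study-day windows.
3. **Post-infusion blood pressure as within-day change**, from the readings at 30 minutes to 12 hours after the end of infusion (4.3.6). Maturation does not affect a change over hours, so this is the cleaner look at an acute effect. Confirm that a pre-infusion reading is available on those days, since that section is partly redacted.

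The cost is wording and programming. Date of birth, gender and gestational age (4.3.1) and the vital-sign readings (4.3.6) are already collected. If the chosen blood pressure norms also need length, check that it is measured close enough to the reading, because the growth schedule in 4.3.9 is partly redacted.

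Downsides: cells may be small, a reference set must be named, and norms for preterm neonates are sparse. Without a control, a shift in age-referenced values still mixes disease course and concomitant drugs with ORGN001.

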14.8.4. Electrocardiograms

Listings of ECG results will be produced.

14.8.5. Electroencephalograms

Listings of EEG results will be produced.

14.9. Pharmacokinetic Analysis

Plasma concentration-versus-time profiles will be graphically summarized. Plasma concentration and PK parameter summaries will include descriptive statistics, as appropriate. [REDACTED]

[REDACTED]

14.10. Other Statistical Issues

14.10.1. Computing Environment

Efficacy and safety analyses will be performed using SAS for windows, Version 9.3 or higher (SAS Institute Inc., Cary, NC, USA).

Pharmacokinetic analyses will be performed using Phoenix WinNonlin Version 6.3 or higher (Pharsight, Cary, NC, USA).

15. DIRECT ACCESS TO SOURCE DATA/DOCUMENTS

15.1. Study Monitoring

A Sponsor's representative or designee may visit the investigational study site to:

- Determine the adequacy of facilities and equipment
- Discuss with the Investigators and other personnel their responsibilities with regard to protocol adherence, and responsibilities of the Sponsor or its representatives. This will be documented in a Clinical Study Agreement between the Sponsor and the Investigator, as appropriate.

During the study, a Sponsor's representative or designee will have regular contact with the investigational site for the following:

- Provide information and support to the Investigators
- Confirm that facilities and equipment remain acceptable
- Confirm that all patients have been properly consented
- Confirm drug accountability
- Confirm that the investigational team is adhering to the protocol, that data are being accurately recorded in the CRFs, and that study drug accountability checks are being performed
- Perform source data verification. This includes a comparison of data in the CRFs with the patient's medical records at the hospital or practice, and other records relevant to the study. This will require direct access to all original records for each patient (eg, clinic charts).
- Record and report any protocol deviations not previously sent to the Sponsor
- Confirm that AEs and SAEs have been properly documented on CRFs, and confirm that any SAEs have been forwarded to the Sponsor. Confirm that SAEs meeting criteria for reporting have been forwarded to the IRB.

The monitor will be available between visits if the Investigators or other staff needs information or advice.

15.2. Audits and Inspections

Authorized representatives of the Sponsor, a regulatory authority, an EC, or an IRB may visit the site to perform audits or inspections, including source data verification. The purpose of an audit or inspection by the Sponsor is to examine systematically and independently all study-related activities and documents, to determine whether study-related activities were conducted, and whether data were recorded, analyzed, and accurately reported, according to the protocol, Good Clinical Practice (GCP) guidelines of the International Conference on Harmonisation (ICH), and any applicable regulatory requirements. The Investigator should contact the Sponsor immediately if contacted by a regulatory agency about an inspection.

15.3. Institutional Review Board/Ethics Committee

The Investigator must obtain IRB/EC approval for the investigation. All IRB/EC approvals, including initial and continued review, and all materials approved by the IRB/EC for this study, including the ICF and any recruitment materials must be maintained by the Investigator and made available for inspection.

16. QUALITY CONTROL AND QUALITY ASSURANCE

To ensure compliance with GCP and all applicable regulatory requirements, the Sponsor or designee may conduct quality assurance audits ([Section 15.2](#)).

17. ETHICS

This study will be performed in accordance with ethical principles that have their origin in the Declaration of Helsinki and are consistent with ICH GCP guidelines.

Investigators and other study personnel must comply with all instructions and regulations specified in this protocol, and applicable ICH GCP guidelines, and must conduct this study in accordance with all local, federal, and regulatory agency regulations.

In accordance with ICH guidelines, pediatric participation in these studies should occur in qualified pediatric centers, with personnel who are properly trained and experienced in studying the pediatric population, and in evaluating and managing potential pediatric AEs. Site personnel should be knowledgeable and skilled in dealing with the pediatric population and its age-appropriate needs, and be encouraged to use measures that minimize discomfort from procedures (eg, topical anesthesia to place IV catheters, use of indwelling catheters rather than repeated venipunctures for blood sampling, and collection of some protocol-specified blood samples when routine clinical samples are obtained).

17.1. Ethics Review

The final study protocol, including the final version of the ICF, must be approved or given a favorable opinion in writing by an IRB or EC, as appropriate. The Investigator must submit written approval to the Sponsor before he/she can enroll any patient into the study.

No modifications to the protocol should be made without the approval of both the Investigator and the Sponsor. Changes that significantly affect patient safety, the scope of investigation, or scientific validity of the study will require IRB/EC notification prior to implementation, except where the modification is necessary to eliminate an apparent immediate hazard to patients. Any deviations from protocol must be fully documented. The Investigator is responsible for informing the IRB or EC of any amendment to the protocol, in accordance with local requirements. In addition, the IRB or EC must approve all advertising used to recruit patients for the study. The protocol must be reapproved by the IRB or EC upon receipt of amendments and annually, as local regulations require.

The Investigator is also responsible for providing the IRB/IEC with any reportable serious adverse drug reactions from any other study conducted with the study drug. The Sponsor will provide this information to the Investigator.

Progress reports and notifications of serious adverse drug reactions will be provided to the IRB or EC, according to local regulations and guidelines.

17.2. Written Informed Consent

The Investigator at each center will ensure that the patient's parent or legal guardian is given full and adequate oral and written information about the nature, purpose, possible risk, and possible benefit of the study. The patient's parent or legal guardian also must be notified that he/she is free to discontinue his/her child from the study at any time. The parent or legal guardian should be given the opportunity to ask questions and time to consider the information provided.

The signed and dated ICF must be obtained before conducting any study procedures.

The Investigators must maintain the original, signed ICF. A copy of the signed ICF must be given to the patient's parent or legal guardian.

Should new information become available during the study that might affect parent or legal guardian willingness to continue study participation, the parent or legal guardian will be notified in a timely manner about the new information and asked to sign a new ICF.

17.3. Patient Data Protection

Prior to performing any study-related procedures, the patient's parent or legal guardian must authorize the release and use of protected health information, as required by local, federal, and regulatory agency law.

Case Report Forms will be completed at the site either on paper or in the electronic data capture (EDC) system. Copies of pertinent records in connection with the study, eg, patient charts or laboratory data, will be made available to the Sponsor or designee on request, in a timely manner throughout the study, with due precaution toward protecting patient privacy.

18. DATA HANDLING AND RECORDKEEPING

18.1. Inspection of Records

The Sponsor or designee will be allowed to conduct site visits for the purpose of monitoring any aspect of the study. The Investigator agrees to allow the monitor to inspect the drug storage area, study drug stocks, drug accountability records, patient charts, study source documents, and other records relative to study conduct.

18.2. Retention of Records

The Investigator must maintain all study-related documentation, in accordance with local retention requirements, for a period of 2 years after the last marketing application approval or, if not approved, 2 years following discontinuation of the test article for investigation. If it becomes necessary for the Sponsor or the regulatory authority to review any study-related documentation, the Investigator must permit access to such records. No records may be destroyed without Sponsor written approval.

